8.1.2. Analysis of Binary Data

Descriptive statistics of binary data will include the number of non-missing observations and frequencies of the observed endpoint as well as the observed proportions. A two-sided 95% CI for the difference in proportions and the corresponding p-value will be provided (when appropriate) using the exact method proposed by Chan and Zhang (1999).

8.1.3. Analysis of Continuous Data

For continuous variables that have skewed data (eg, cumulative IV opioid use, hourly and daily opioid use), the data will be rank-transformed and ANCOVA, with the covariates of Age Group (for analyses of Cohort 1 and Cohort 2 combined) and Genotype (for all analysis groups), will be used to obtain p-values for the hypothesis of interest. The difference between medians of the untransformed data will be used to estimate the treatment effect. A bootstrap (with stratification by Age Group and Genotype) 95% confidence interval for this difference in medians will be reported.

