- Distribution of TTRFD is exponential.
- Median times to readiness-for-discharge are 156 and 106 hours, for the placebo and rivipansel groups, respectively (based on observed data in the Phase 2 trial).

- The stratified log-rank test is used to test the statistical hypothesis in the primary efficacy analysis, in support of the primary objective of the study.
- Alpha=0.05 (two-sided test), power=0.90.

Based on above assumptions, a total of at least 300 subjects should be enrolled into Cohort 1 and Cohort 2 combined and at least 282 events observed, in order to have at least 90% power for the primary efficacy analysis conducted on data from Cohort 1 and Cohort 2 combined.

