10.1.3. Daily IV Opioid Use

In this study, subjects may receive study drug for up to 8 days (up to 15 doses of study drug: 1 loading dose and a maximum of 14 maintenance doses). In the Phase 2 study, 79% of subjects were discharged from hospital within 8 days. Therefore, daily IV opioid use will be analyzed from Day 1 through Day 8. The subject's daily opioid use will be the total amount of opioid used in increments of 24 hours starting at the start of the first infusion (loading dose) of study drug and continuing for the entire duration of the subject's hospitalization or through the Day 8 / Hour 24 time point. The amount of IV opioid received will be standardized using morphine equivalent units (MEU) and normalized by the subject's body weight (see [Section 10.1.1](#)). A subject will be assigned an IV opioid use of 0 for any day in which the subject did not receive any IV opioids. For subjects who are discharged before Day 8, the subject's daily IV opioid use will be assigned a value of 0 for any 24-hour interval within the 8-day period that occurs after the subject has been discharged from hospital.

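### For daily IV-opioid use, a difference in raw medians is likely to be exactly 0 on Day 8, and possibly Day 7, even when the arms differ; an added estimate is needed for those days

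*SAP*

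**What the plan says.** SAP 8.1.3 covers continuous variables with skewed data and names daily opioid use among them ("eg, cumulative IV opioid use, hourly and daily opioid use), the data will be rank-transformed"). The test is an ANCOVA on ranks. The effect estimate is separate: "The difference between medians of the untransformed data will be used to estimate the treatment effect", with a 95% bootstrap interval stratified by age group and genotype.

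SAP 10.1.3 defines the variable in 24-hour intervals from the start of the loading dose. It notes that "In the Phase 2 study, 79% of subjects were discharged from hospital within 8 days", and continues: "Therefore, daily IV opioid use will be analyzed from Day 1 through Day 8". There are two sources of zeros:

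- In hospital: "A subject will be assigned an IV opioid use of 0 for any day in which the subject did not receive any IV opioids".
- After discharge before Day 8: "daily IV opioid use will be assigned a value of 0 for any 24-hour interval within the 8-day period".

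SAP 8.1 also asks for the mean, standard deviation, median, minimum and maximum of continuous variables. No visible text gives another effect estimate for daily use.

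**The concern.** A median does not respond to anything in the upper half of the data once more than half the values are 0. SAP 10.1.3 itself expects most subjects to have left hospital by the end of the 8-day window. Late in that window both arms can therefore have a median of 0, and the difference is then 0 whatever the remaining subjects receive. The rank test still sees that more placebo subjects are on IV opioids, so one table row can carry a small p-value, an effect of 0 and an interval that includes 0. A reader cannot tell from such a row how large the difference was.

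**Working it through.** **The plan's own figure.** With medians of 156 and 106 hours, two-sided alpha 0.05 and 90% power, the Schoenfeld formula gives 4 × (1.960 + 1.282)² / [ln(106/156)]² = 4 × 10.507 / 0.1493 = 281.5, so 282 events. This matches SAP 4.1, and the same assumptions are used below.

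**Inputs from the documents.**

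- SAP 4.1: "Median times to readiness-for-discharge are 156 and 106 hours, for the placebo and rivipansel groups, respectively" and "Distribution of TTRFD is exponential".
- 300 subjects randomised 1:1, so about 150 per arm.
- SAP 6.1.1: stopping IV opioids is readiness criterion C3, so it cannot fall after readiness.

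**Assumptions not in the documents.** The lag L between stopping IV opioids and readiness is taken as 0, 12 or 24 hours. A Weibull with shape 2 and the same medians is an alternative to the exponential. Subjects receive IV opioid every day until they stop; days without it in between would only add zeros.

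**Step 1, share with any IV opioid on Day d.** Day d starts at 24(d − 1) hours. With t = 24(d − 1) + L, the share is S(t) = 2^(−t/m) for the exponential and 2^(−(t/m)²) for the Weibull, where m is the arm's median. For Day 8 with L = 0, the exponential gives 2^(−168/156) = 47.4% for placebo and 2^(−168/106) = 33.3% for rivipansel.

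**Step 2, chance that the effect is exactly 0.** With 150 values, the median is the average of the 75th and 76th in order, so it is 0 only if at least 76 values are 0. For placebo on Day 8, P[Binomial(150, 0.526) ≥ 76] = 0.711. For rivipansel it is essentially 1. The product is 71%.

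| Day | Lag (h) | Exponential | Weibull shape 2 |
|---|---|---|---|
| 6 | 0 | 1% | 0% |
| 7 | 0 | 22% | 8% |
| 7 | 12 | 47% | 47% |
| 7 | 24 | 71% | 89% |
| 8 | 0 | 71% | 89% |
| 8 | 12 | 88% | 99% |

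The 12-hour threshold for Day 7 follows from the planning median: 144 + 12 = 156 hours, where the placebo share is exactly 50%.

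**Step 3, how far the arms differ on Day 8 (no lag).** The share on IV opioids differs by 47.4 − 33.3 = 14.1 points under the exponential and by about 27 points under the Weibull. If the dose per hour is the same in both arms, mean daily use is proportional to the average share over hours 168 to 192. Under the exponential this is about (0.474 + 0.426)/2 = 0.450 for placebo and (0.333 + 0.285)/2 = 0.309 for rivipansel, so the rivipansel mean is about 31% lower (0.141/0.450).

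**Step 4, p-value and effect together.** Trials were simulated with 150 per arm, an assumed lognormal dose, a t-test on ranks in place of the rank ANCOVA, and no lag. On Day 8 the rank test gave p < 0.05 in about 70% of exponential trials and 100% of Weibull trials. In about 40% and 90% of all trials respectively, p < 0.05 stood beside an effect of exactly 0. The bootstrap interval for the median difference included 0 in 99% to 100%.

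**Sensitivity to shorter stays.** The planning exponential implies that only (57.4% + 71.5%)/2 = 64% are ready by 192 hours, against 79% discharged within 8 days in Phase 2. An exponential rescaled to 79% with the same ratio of medians (about 102 and 70 hours) gives an effect of exactly 0 in about 90% of trials on Day 6 and nearly all on Days 7 and 8.

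**The case against.** The strongest reply is that a median difference of 0 is a correct value of the quantity the SAP chose, and that the information is available elsewhere. Arm means are shown descriptively under SAP 8.1. Time to discontinuation of IV opioids and cumulative IV-opioid consumption are both key secondary endpoints. Daily use is not among the visible primary or secondary endpoints, and the sections likely to describe its analysis are blacked out. A mean is also open to challenge: heavy users can dominate it, and in the exponential simulations its interval excluded 0 on Day 8 in only 24% to 53% of trials.

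Most of this stands and limits the point. It does not remove it. SAP 8.1.3 names daily use and fixes the effect estimate and interval that sit beside the p-value, and descriptive arm means carry no interval for the difference. The redacted text may contain another summary, but that cannot be assumed.

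A reader might infer three stronger things, none of which is supported:

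- That the effect is usually 0 throughout the last treatment days. Under the planning medians with no lag this holds for Day 8 only. On Day 7 the estimate is non-zero in 78% to 92% of trials, and Day 6 is essentially untouched.
- That the later opioid benefit cannot be expressed. Day 7 carries nearly the same difference in shares (52.7% against 39.0%, 13.7 points), and the two key secondary endpoints also capture it.
- That the bootstrap interval is invalid. An interval that includes 0 is what a median difference of 0 should produce, and no coverage failure has been shown.

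**Conclusion.** The point holds for Day 8, and possibly for Day 7. Under the planning medians with about 150 per arm, the Day 8 effect is exactly 0 in about 71% to 89% of trials if IV opioids stop at readiness. Because they cannot stop later than readiness, that is the case most favourable to the plan. Day 7 depends on the undocumented lag: 8% to 22% with none, 47% at 12 hours, 71% to 89% at 24 hours. Stays shorter than planned would extend the problem.

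The Day 8 range rests on the planning medians, the choice of exponential or Weibull shape 2, and uninterrupted daily use until stopping; it does not depend on the dose distribution. The frequency of a significant p-value beside a zero effect comes from simulation with an assumed dose distribution. What is affected is the reported size of effect for a supportive variable. The fixed-sequence tests and all confirmatory conclusions stay as they are.

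**What to change.** In SAP 8.1.3, for daily IV-opioid use, keep the rank ANCOVA and the median difference, and add for each day:

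1. The percentage of subjects receiving any IV opioid, by arm, with the difference and 95% confidence interval by the exact method of SAP 8.1.2. Under the planning exponential with no lag this would show 14.1 points on Day 8.
2. The difference in means, with the same stratified bootstrap 95% interval. SAP 8.1.1 already uses a mean difference for time-to-event endpoints, so this fits the plan's own practice.

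State that these two are the effect estimates to read on any day when either arm has more than half zeros. Cumulative and first-24-hour consumption need no change on this account.

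The cost is a short addition to the SAP, a small programming change and slightly more output, all from data already collected. The drawback is that means are sensitive to heavy users, so the percentage should be read alongside them.

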8.2. STATISTICAL ANALYSES

8.2.1. Primary Endpoint Analysis

Analysis of the primary endpoint TTRFD will be performed using the FAS and the methods described in [Section 8.1.1](#) with specific details provided below. The primary endpoint will be analyzed in Cohort 1 and Cohort 2 combined (as the primary analysis population), as well as Cohort 1 (alone and by age group) and Cohort 2 separately.

Cohort 1 and Cohort 2 Combined:

Primary Efficacy Analysis: The primary analysis will consist of a stratified log-rank test to compare the survival distributions of the primary endpoint TTRFD between the rivipansel and placebo groups, where the stratifications are age group and genotype. The trial will meet the primary objective if this stratified log-rank test is statistically significant using an alpha of 5% (ie, 2-sided log-rank test p-value ≤ 0.05).

8.2.2. Key Secondary Endpoint Analysis

A fixed-sequence approach will be used to control overall Type I error for the primary and key secondary endpoints at 0.05 for Cohort 1 and Cohort 2 combined. Please see [Section 4.2](#) for details. Analyses of all key secondary endpoints are based on the FAS.

1. Time to discharge (in hours) will be analyzed in the same manner as the primary endpoint using the methods described in [Section 8.1.1](#) except that analyses will not be performed for Cohort 1 alone.
2. Cumulative IV opioid consumption (in MEU/kg) will be analyzed using an ANCOVA model as described in [Section 8.1.3](#), using rank-transformed cumulative IV opioid consumption data. This endpoint will not be analyzed for Cohort 1 alone.
3. Time to discontinuation of IV opioid (in hours) will be analyzed in the same manner as the primary endpoint using the methods described in [8.1.1](#) except that analyses will not be performed for Cohort 1 alone.

8.2.3. Sensitivity Analyses

To support the interpretation of the analyses of the primary and key secondary endpoints (described in [8.2.1](#) and [8.2.2](#)), robustness or sensitivity analyses will be performed.

The alternative definition of date and time when C1/C2 are met would result in

8.2.4. Other Secondary Endpoints Analysis

Analyses of all of the secondary endpoints for Cohort 1 and Cohort 2 combined and for Cohort 1 by Age Group and Cohort 2 separately are based on the FAS.

- Cumulative IV opioid consumption in MEU/kg within the first 24 hours post-loading dose of study drug (See Appendix [Section 10.1.1](#) for details).

This endpoint will be analyzed using an ANCOVA model as described in [Section 8.1.3](#), using rank-transformed endpoint data.

- Percent of subjects re-hospitalized for VOC within 3 days of discharge

This endpoint will be analyzed using the statistical methods for binary endpoints described in [Section 8.1.2](#).

8.5. Analysis of Safety Data

For Cohort 1 and Cohort 2 combined, Cohort 1 by age group and Cohort 2 alone based on the Safety Analysis Set, the safety data (eg, AEs, SAEs, vital signs, physical examinations, laboratory tests) will be summarized in accordance with CDISC and Pfizer Standards (CaPS). In addition, for Cohort 1 and Cohort 2 combined ONLY, a 3-tier approach described below will be used for summarizing AE data. Safety data that will be specifically summarized include:

- Adverse events:

[figure not shown]
The analyses of adverse events will make use of the 3-tiered approach described below for Cohort 1 and Cohort 2 combined ONLY. These analyses will be considered exploratory. Under the 3-tier approach, AEs are classified into one of three tiers with different analyses performed for different tiers.

- Tier-1 events: These are events that are pre-specified events of clinical importance and are maintained in the custom AE term list system (CAETeLiSt).
- Tier-2 events: These are events that are not tier-1 but are “common”. A MedDRA Preferred Term (PT) is defined as a Tier-2 event (“common” event) if there are at least 4 in any treatment group.
- Tier-3 events: These are events that are neither tier-1 nor tier-2 events. Tier-3 events will be reported with observed proportions by treatment group without comparative statistics.

For Tier-1 events, the unconditional exact method for 95% CI for risk difference and p-value proposed by Chan and Zhang (1999) will be used to compare rivipansel with placebo. For Tier-2 events, the normal approximation will be used for calculating the 95% CI for risk difference. There will be no adjustment for multiple comparisons or stratification factors in the analyses.

- Safety laboratory tests reported according to CDISC and Pfizer standards (CaPS). Shift tables summarizing the changes in laboratory test results from baseline will be presented (see Appendix [Section 10.3](#) for details on shift tables).
- Incidence of clinically significant changes in physical examination will be summarized using descriptive statistics.
- Change from baseline at End of Treatment and at the Day 35 Post-discharge Visit in vital signs (eg, blood pressure, heart rate, temperature, respiratory rate, and pulse oximetry) will be reported using descriptive statistics.
- Incidence of adjudicated AEs will be analyzed using the same approach as for Tier-1 events.

- Percentage of subjects re-hospitalized for VOC within 7, 14 and 30 days of discharge will be summarized using descriptive statistics.
- AE data (Summary of TEAE-all causality, TEAE-all causality, TE-SAE-all causality) will be also reported for the following 3 non-age subgroups: Genotype, Hydroxyurea use at baseline and Gender based on the safety analysis set in Cohort 1 and Cohort 2 Combined.

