9.4. Safety Analysis

The safety data (eg, AEs, SAEs, physical exams, laboratory tests, vital signs) will be summarized in accordance with the Clinical Data Interchange Standards Consortium (CDISC) and Pfizer Standards (CaPS). Safety data that will be specifically summarized include:

- Adverse events according to CaPS;
- Safety laboratory tests according to CaPS;
- Physical exams and vital signs assessments according to CaPS;
- Incidence of adjudicated ACS and incidence of adjudicated severe and/or generalized cutaneous manifestations analyzed using exact methods.
- Percent of subjects re-hospitalized for VOC within 7, 14 and 30 days of discharge analyzed using exact methods.

The safety analysis set will be all subjects who receive at least one infusion of study drug.

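### Protocol 9.4 assigns exact methods to VOC re-hospitalisation within 7, 14 and 30 days of discharge; SAP 8.5 assigns the same endpoints only descriptive statistics, and no visible text explains the difference

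*SAP*

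**What the plan says.** Protocol 9.4 lists, among the safety data to be summarised: "Percent of subjects re-hospitalized for VOC within 7, 14 and 30 days of discharge analyzed using exact methods". It gives the same instruction for adjudicated ACS and adjudicated cutaneous events. Protocol 9.2.4 also assigns exact methods to re-hospitalisation within 3 days, which is an efficacy endpoint there.

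SAP 6.2 repeats the 7-, 14- and 30-day percentages as safety endpoints, with the same windows as Protocol 2.2.2. For their analysis, SAP 8.5 says: "Percentage of subjects re-hospitalized for VOC within 7, 14 and 30 days of discharge will be summarized using descriptive statistics".

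The SAP treats the neighbouring items differently:

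- Adjudicated events, SAP 8.5: "Incidence of adjudicated AEs will be analyzed using the same approach as for Tier-1 events". Tier 1 is the Chan and Zhang unconditional exact 95% CI and p-value for the risk difference.
- 3-day readmission, SAP 8.2.4: "This endpoint will be analyzed using the statistical methods for binary endpoints described in" Section 8.1.2.
- Binary data in general, SAP 8.1.2: "Descriptive statistics of binary data will include the number of non-missing observations and frequencies of the observed endpoint as well as the observed proportions". A separate sentence follows: "A two-sided 95% CI for the difference in proportions and the corresponding p-value will be provided (when appropriate) using the exact method" of Chan and Zhang.

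**The concern.** The two current documents name different analyses for the same endpoints, and a programmer or reader cannot tell which is planned.

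The primary endpoint rewards earlier readiness for discharge, and time to discharge is tested next in the fixed sequence. Readmission for VOC in the following weeks is the natural check that a shorter stay is not bought with an early return. Protocol 1.2.3 reports that re-hospitalisation for VOC was the most common SAE in both Phase 2 groups. Two percentages side by side do not show how large an excess on rivipansel the data leave open; an interval for the difference does.

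**Working it through.** **Comparison of the texts**

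| Endpoint | Protocol | SAP |
|---|---|---|
| VOC readmission within 3 days | Exact (9.2.4) | Binary methods of 8.1.2, exact CI where appropriate (8.2.4) |
| Adjudicated ACS and cutaneous events | Exact (9.4) | Tier-1 approach, exact CI and p-value (8.5) |
| VOC readmission within 7, 14 and 30 days | Exact (9.4) | Descriptive statistics (8.5) |

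Only the last row differs. Descriptive statistics cannot easily be read as including the exact interval, because SAP 8.1.2 puts counts and proportions in one sentence and the exact CI in another. SAP 8.5 does not refer to 8.1.2 for these windows. The visible rows of the version 5 change table (SAP Section 1, Table 2) do not mention the change.

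**What an interval would show**

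The documents give no readmission rate, so this part is an illustration.

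- Arm size: 300 randomised 1:1 (Protocol 3.2 and 5.1), so 300 / 2 = 150 per arm. A second case of 140 per arm is assumed, to allow for subjects not treated or not discharged.
- Observed rates: assumed equal in the two arms, at 10%, 20% and 30%, with two lower cases added.
- Method: Chan and Zhang exact 95% CI, the method named in the SAP. For a difference d, the statistic is T(d) = (p̂₁ − p̂₂ − d) / √{[p̃₁(1 − p̃₁) + p̃₂(1 − p̃₂)] / n}, where p̃₁ and p̃₂ are the maximum-likelihood rates under p₁ − p₂ = d. The upper limit is the d at which the one-sided probability of a T at or below the observed value, maximised over the unknown placebo rate (400-interval grid), falls to 2.5%. With equal counts the interval is symmetric about zero.
- Comparison: the Wald half-width, 1.96 × √[2p(1 − p) / n]. For 30/150 this is 1.96 × √(2 × 0.2 × 0.8 / 150) = 1.96 × 0.0462 = 9.05 points.

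| Events per arm | Rate | Exact 95% limit (± points) | Wald (± points) |
|---|---|---|---|
| 3/150 | 2.0% | 4.0 | 3.2 |
| 8/150 | 5.3% | 5.6 | 5.1 |
| 15/150 | 10% | 7.11 | 6.79 |
| 30/150 | 20% | 9.23 | 9.05 |
| 45/150 | 30% | 10.45 | 10.37 |
| 14/140 | 10% | 7.39 | 7.03 |
| 28/140 | 20% | 9.59 | 9.37 |
| 42/140 | 30% | 10.83 | 10.74 |

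For example, 30 readmissions in each arm of 150 would look identical in a descriptive table, yet would be compatible with an excess of about 9 points on rivipansel.

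**Number of intervals**

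SAP 8.5 covers four populations: "For Cohort 1 and Cohort 2 combined, Cohort 1 by age group and Cohort 2 alone based on the Safety Analysis Set", that is, combined, 12-17, 18 and over, and 6-11 years. An exact interval in every population would mean 3 windows × 4 = 12. The tiered approach is limited to one population ("In addition, for Cohort 1 and Cohort 2 combined ONLY, a 3-tier approach described below will be used for summarizing AE data"), which gives 3 × 1 = 3.

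**The case against.** **The SAP may depart from the protocol.** Protocol Section 9 allows this and asks for an amendment only for major modifications. Lighter reporting of three safety windows may be a deliberate and minor choice. The changes and rationales for SAP versions 2 to 4 are redacted, as are two rows of the version 5 change table; SAP 8.3, 8.4 and most of 8.2.3 are not visible. This stands. A reader might infer that the exact analysis was dropped by oversight, or in breach of the protocol; the documents support neither. What remains is that the current protocol still says exact and the current SAP says descriptive.

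**An interval is not ruled out.** Also correct. Protocol 9.4 names no specific exact method and no between-arm interval. The general text of SAP 8.1.2 could be applied here, although its exact CI is given only where appropriate, a condition that also qualifies the 3-day analysis. The visible text does not assign an exact analysis to these windows, but it does not forbid one.

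**VOC return is partly covered elsewhere.** The 3-day window goes to SAP 8.1.2. Each VOC re-hospitalisation in follow-up is also an SAE (Protocol 8.6.1), and Tier 2 needs only 4 events in any treatment group, so a between-arm CI for a VOC preferred term is likely in the combined population if the events code to one term. It would therefore be too strong to infer that readmission goes unexamined. But a preferred-term interval spans the whole AE period and does not show when the return occurred, and Tier-2 intervals use a normal approximation.

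**The widths do not measure harm.** They describe the precision of the trial under assumed rates. The counts would be reported either way, and a reader could calculate an interval from them. This stands, and it limits the severity.

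**Conclusion.** The mismatch is literal and sits in current text. Confidence is high for the difference in wording, but not for any view of why it arose.

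The impact is minor. These are safety endpoints outside the fixed sequence, so the primary analysis, type I error and sample size do not change. What is lost is a planned statement of the excess in readmission that the data leave open in each window: about 7 to 10 points under assumed equal rates of 10% to 30% with 150 per arm, slightly more with 140, and about 4 to 6 points at rates of 2% to 5%. The 30% SAE rate in Phase 2 covers all SAEs in subjects aged 12 to 60. It is context for the range, not a bound on VOC readmission in a trial that also enrols ages 6 to 11.

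**What to change.** In SAP 8.5, keep the descriptive summary of the three windows and extend the sentence along these lines:

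> … and, for Cohort 1 and Cohort 2 combined, analysed with the Tier-1 approach (Chan and Zhang exact 95% CI for the risk difference); these analyses are exploratory and without multiplicity adjustment.

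This uses a method already in the section, treats the windows like the adjudicated events, and leaves the age-group and Cohort 2 results descriptive. The Tier-1 approach includes a p-value; a special rule to suppress it here would create a new inconsistency, and the exploratory label is enough. If descriptive reporting alone is intended, align Protocol 9.4 with the SAP and record the reason.

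The cost is one sentence and three intervals, with no new data. The downside is that the intervals are unadjusted and the windows are nested: a subject readmitted within 7 days also counts at 14 and 30 days. The three results must not be read as independent.
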